#### Financial aspect

Hypothesis: The extended triage intervention leads to an overall reduction in expenditures for the Health Insurance System (HIS) and the patient. The size of this reduction is determined by the presenting complaint (eMTS flowchart and urgency category), diagnosis, time of the day and patient characteristics.

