#### Research questions

- 9. What is the difference in average expenditures per patient for the Health Insurance System (HIS) and for the patient between intervention and control weekends for ambulatory patients presenting at the ED (and seen at the ED or at the GPC)?
- 10. What is the difference in average expenditures per patient for the HIS and for the patient between intervention and control weekends for different patients groups:
  - 10.1. Patients coded in the two least urgent categories (green and blue) presenting at the ED (and seen at the ED or at the GPC?
  - 10.2. Patients coded in the two most urgent categories (red and orange) presenting and treated at the ED?

- 11. For which type of medical treatment expenditures (consultation fees, medical imaging, clinical biology...) is there a difference between the control weekends and the intervention weekends (for patients described in 9 and 10)?
- 12. What are the determinants of treatment costs?

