#### Design of the clinical trial

#### A controlled longitudinal prospective intervention trial

To answer the above-mentioned research questions we need a longitudinal prospective intervention trial.

To allow definitive conclusions for our questions we need a control group. Historical controls will have too much confounding (not all data is available, the ED was organised in a different way, the GPC was unknown for many patients). Individually randomised controls are impossible from a practical point of view and because of contamination (patients will talk to each other and will not understand why some get a GPC advice and others not). Finally, randomisation by shift is not possible because they overlap in time. Therefore, randomisation is only possible by weekend. We will roll out one control weekend out of every four intervention weekends.

During a control weekend, all data registration and collection will be the same as during intervention weekends but we will not inform patients about their allocation advice. The emergency physician will see all patients deciding to stay at the ED, without influence of the triage advice. As in standard clinical care, patients will have the right to change their mind and go spontaneously to the GPC. Another difference is the communication to the patient: during intervention weekends, we will inform them about the intervention using leaflets and broadcasting in the waiting room of the ED. During control weekends, we will only inform about MTS-triage in general but no about the GPC. We will always mention the iCAREdata opting-out procedure.

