#### **Inclusion and Exclusion**

We will systematically include all patients presenting at the ED during the weekend (the GPC is only open during the weekend starting from Friday 7 pm until Monday 6 am). By presentation at the ED we mean the patient is registered by the receptionist of the ED as a patient. Patients who just pass the ED to enter the hospital or who go directly to a medical department (e.g. obstetrics) are thus not included. The availability of a Belgian citizen national insurance number is the only inclusion criterion. This number is necessary to send the data needed for this study to the iCAREdata database. For the vast majority of patients this number is available. It will not be available for patients who present for the first time at the hospital and forgot all official documents. For patients without a Belgian identity (foreign citizens without Belgian health insurance, people without a legal status and babies less than one week old) the number is never available. The EDs own software allows us to calculate the number of excluded patients.

Patients arriving at the ED by an ambulance with a doctor or nurse (in Dutch called MUG or PIT) is the only exclusion criterion (these patients have already passed through a sort of triage). We estimate an exclusion rate of 15 patients per weekend.

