# Methodology for the financial aspects

Resources are scarce and therefore it is essential to look at both outcome and resource use when introducing new treatments or treatment paths. This project incorporates both sides. We will use HIS expenditure data (including the share paid by the patient) to get a first insight in the changes in resource use due to the extended triage. Expenditures will be limited to the expenditures of the OOH consultation. In this way, we gain insight in the short-term impact of the new triage system on medical costs from the point of view of the patient and the HIS. For this aspect, we only focus on ambulatory patients (not admitted to the hospital). Although some inpatients can also present at the ED; admitted patients have far more complicated costs and they are not the focus of this project.

In our research we will make use of a cluster randomized trial to get an unbiased estimate of the difference in expenditures due to the extended triage. Randomization allows to measure the impact of the extended triage on average expenditures per patient (research question 9) or specific types of average expenditure per patient (research question 11) by comparing these average expenditures per patient between the intervention weekends and the control weekends. Information on the expenditures of consultations of the GPC are collected in the iCAREdata database. Expenditures generated by the ED are not yet routinely collected for research purposes, but billing data are available and these will be used. We will calculate the averages and use a t-test to test statistical significance. Medical bills also contain detailed information of the nomenclature codes (these are the codes used by the HIS, describing reimbursed care and reimbursement tariffs), performed during an ED visit. We will aggregate these interventions in similar groups such as consultation fees, medical imaging, clinical biology and so on. We will then compare these average expenditures per patient for the various aggregates between the intervention weekends and the control weekends (research question 10) and use a t-test for statistical significance.

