Currently, the ED's software package sends all nomenclature codes except those for clinical biology and medical imaging to the financial department of the hospital, where the actual bills are made. The financial department draws up the bill, taking into account regulations; e.g. sometimes, regulation prohibits to bill two nomenclature codes simultaneously; the department then decides which one to charge.

To gain more insight in differences in expenditures for different patient groups (research questions 9 and 11), we need demographic and medical diagnostic information of the patient, which is not available on the invoices and is not accessible by the financial department of AZ Monica. We will therefore proceed as follows. We will make a table of all included patients with the following columns: time of arrival at the ED, year of birth, gender, ZIP-code and a new serial number created by us. We will transfer these data using encrypted messages. Because the financial department already has these data to make the invoices this does not raise any new privacy issues. The financial department will search for these included patients and deliver us a datasheet with all the information of the actual invoices linked to this new serial number but without any additional personal data. The nomenclature codes of the interventions performed at the ED can be transferred using iCAREdata.

If the reconstructed bills prove to be valid, research questions 10.1, 10.2. and 12 can be addressed with the variables collected in iCAREdata. For questions 10.1 and 10.2, we will calculate expenditures per patient (for the HIS and the patient) for urgency categories blue and green separately, and for urgency categories red and orange and compare them between the intervention and control weekends, using a t-test to test for statistical difference.

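### Limiting the cost comparison to patients not admitted conditions on an event after randomisation, so the claimed unbiased cost difference is not secured

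*Combined protocol and SAP*

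**What the plan says.** Under the heading on the controlled longitudinal design, the unit of assignment is the weekend: "Therefore, randomisation is only possible by weekend". Under Inclusion and Exclusion the study population is broad: "We will systematically include all patients presenting at the ED during the weekend". A national insurance number is required, arrival by an ambulance with a doctor or nurse excludes, and later admission plays no part.

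The Financial aspect section sets a broad hypothesis: "The extended triage intervention leads to an overall reduction in expenditures for the Health Insurance System (HIS) and the patient". Question 9 is narrower and is posed "for ambulatory patients presenting at the ED (and seen at the ED or at the GPC".

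The Methodology for the financial aspects extends the restriction to the whole cost analysis: "For this aspect, we only focus on ambulatory patients (not admitted to the hospital". The reason given is practical: "admitted patients have far more complicated costs and they are not the focus of this project". The same section limits expenditure to the out-of-hours (OOH) consultation. It then says that the cluster randomised design serves "to get an unbiased estimate of the difference in expenditures due to the extended triage", with averages per patient compared by t-test. On invoice data it says: "We will make a table of all included patients with the following columns".

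**The concern.** Randomising weekends makes the two groups comparable on everything settled before the advice is given. Admission is settled later. If the intervention changes who is admitted, the non-admitted patients in the two kinds of weekend are no longer the same kind of patient. Part of any cost difference is then a difference in mix.

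A second problem does not depend on any change in the admission rate. A patient who follows GPC advice, is referred back to the ED and is admitted has used two OOH contacts. The protocol gives wrongly diverted patients special attention for safety, but the cost analysis leaves out those among them who are admitted. An average over ambulatory patients does not test a claim about overall expenditure.

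At stake is the causal reading of questions 9 to 11. The primary outcome and the safety questions are not affected.

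**Working it through.** The documents give no admission rate, diverted share, cost or standard deviation for the cost comparison, so there is no planned figure to reproduce. The check has two parts: the logic, and an illustration with assumed inputs.

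**Can the intervention change admission?** The primary hypothesis is that more patients will be seen by a GP instead of an emergency physician. The discussion of false positives foresees diverted patients being referred back, and time being lost. Either could change who is admitted. No passage argues that admission is unaffected.

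**Does the plan check or repair this?** None of questions 1 to 12 compares admission between weekend types. The comparisons for questions 9 to 11 are unadjusted t-tests. The regression for question 12 has patient, triage and system covariates, but nothing that addresses admission. No sensitivity analysis includes admitted patients.

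**Illustration of size.** Inputs, all assumed, with the cost of an ambulatory ED contact set to 1:
- 15% of included patients admitted on control weekends, so 85% are ambulatory
- 20% of included patients diverted to the GPC and not admitted on intervention weekends, so 85% − 20% = 65% are ambulatory at the ED
- cost of a GPC contact: 0.4
- s: fall in the admission share on intervention weekends
- c: cost of the patients who are no longer admitted

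Apparent relative difference = (0.65 + 0.20 × 0.4 + s × c) / (0.85 + s) − 1 = (0.73 + s × c) / (0.85 + s) − 1.

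- No change in admission (s = 0): 0.73 / 0.85 − 1 = −14.1%.
- s = 0.01, c = 0.4: 0.734 / 0.86 − 1 = −14.7%. The saving is 14.65 / 14.12 = 1.038 times the base, about 4% larger.
- s = 0.02, c = 0.4: 0.738 / 0.87 − 1 = −15.2%. The saving is 15.17 / 14.12 = 1.075 times the base, about 8% larger.

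The value c = 0.4 follows the route the documents describe: a diverted patient is seen by a GP and is not admitted, so the cost is a GPC contact.

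**How large a shift is this?** From the 8000 weekend presentations in 2016 and 15 exclusions per weekend, (8000 − 15 × 52) / 52 = 138.8 patients per weekend. One to two points is 1.4 to 2.8 patients per weekend. As a share of those diverted it is 0.01 / 0.21 = 4.8% to 0.02 / 0.22 = 9.1%, which is not negligible for a low-urgency group.

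**Patients referred back and admitted.** On the same scale each has a cost of about 0.4 + 1 = 1.4. The mean of the retained intervention patients in the base case is 0.73 / 0.85 = 0.86. If such a patient would not have been admitted on a control weekend, leaving the patient out makes intervention weekends look cheaper than they were. If the patient would have been admitted anyway, the extra GPC contact (0.4) is still lost from the overall account. The documents give no count of these patients, so no percentage is attached.

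**After the change.** If every included triaged patient stays in the denominator with OOH-contact expenditure, the selection term is zero by construction, whatever the admission shares.

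**The case against.** The strongest defence is that the restriction is a disclosed choice of target. Question 9 is posed for ambulatory patients, and the methodology describes its aim as a first insight into short-term impact. Only green and blue patients can be allocated to the GPC and the eMTS is described as risk averse, so the patients whose path changes should rarely be near admission. This stands as a reason to expect a small effect. It does not support the word unbiased, which needs admission to be unaffected, and the plan neither argues that nor sets out to check it.

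A reader might infer that the comparison is shown to be biased, or badly so. The documents do not support that. They show a possible route, not a change in admission. A reader might also put costly values into the formula. With s = 0.01 and c = 2 the saving falls to 12.8%, about 9% smaller. With s = 0.02 and c = 3 it falls to 9.2%, about 35% smaller. Those cases need patients costing two to three ED contacts to stop being admitted. A diverted patient seen by a GP does not fit that description, and no other route is documented.

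The practical reason for the restriction also has some force. Expenditure is limited to the OOH consultation, so inpatient costs would not be counted in any case. But the ED part of an admitted patient's invoice may be hard to isolate: the financial department applies billing rules when two codes cannot be charged together, and the ED software does not send imaging and clinical biology codes. The statement that the table covers all included patients stands in a section limited to ambulatory patients, so it does not prove that invoices of admitted patients will be requested.

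**Conclusion.** The concern holds in limited form. For questions 9 to 11 the plan conditions on an event that follows assignment and that the intervention may change, so the unbiased estimate it claims is not secured. The ambulatory-only average also does not test the hypothesis of an overall reduction, because it omits diverted patients who were referred back and admitted.

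Size and direction cannot be determined from the documents. The selection bias is zero if admission does not respond, and may be small given the limit to green and blue patients. The figure of about 4% to 8% of the saving rests entirely on the assumed 15% admitted, 20% diverted, cost ratio of 0.4 and a fall in admission of 1 to 2 points confined to diverted patients. The conclusion that the estimate is biased, as opposed to unprotected, goes further than the text allows.

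**What to change.** Cheap improvement, in three parts.

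1. Report the proportion admitted by weekend type, overall and for green and blue at triage.
2. Add a comparison of OOH-contact expenditure (GPC plus ED lines, without the inpatient stay) in all included triaged patients, and in those green or blue at triage for question 10.1. Let this comparison carry the claim of an unbiased difference wherever ED lines can be separated for admitted patients. Where they cannot, give bounds: a lower one counting none of the unassignable lines to the ED contact and an upper one counting all of them.
3. Keep the ambulatory-only comparison, label it as conditional on non-admission, and remove the word unbiased from it.

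The plan should state explicitly that the table sent to the financial department includes admitted patients. ED nomenclature codes can already come through iCAREdata, so the extra work lies mainly in the imaging and clinical biology lines of admitted patients. The other cost is statistical: including admitted patients makes expenditure more variable and the estimate less precise.

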# Methodology for the medical aspect

The data necessary for this work package are part of a routine clinical report. We will use three types of these reports: triage-consultation reports, ED consultation reports and GPC consultation reports. We will collect these data using the iCAREdata database. This database can link our three types of clinical reports using an irreversibly coded national number. Due to data protection rules, the iCAREdata data manager will execute all queries and only aggregated results will be transferred to the researchers. For more complex statistical analysis, the data manager will transfer an analysis specific table or the analysis will be carried out on the computer of the data manager in cooperation between the researcher and the data-manager. A detailed data management plan is available. The correctness of a triage decision depends on the patient's situation:

- At the GPC (patients compliant to a GPC advice or non-compliant to an ED advice): the ratio of patients referred to an ED to the total number of patients coming from the ED of AZ Monica.
- At the ED (patients compliant to an ED advice or non-compliant to a GPC advice): the physician will answer the same question for all patients: "Should this patient better go to the GPC?". The correctness is defined as the ratio of the patients with a positive answer to this question to the total number of patients staying at the ED after triage.

The parameters of interest in questions 1 through 8 are (conditional) proportions, which calls for analysis by a non-linear model (e.g. binary logistic regression). The study design results in the creation of nested data, where patients are nested in weekends, and weekends are nested in (multiple) nurses. Appropriate analysis of such auto-correlated data requires a nonlinear mixed model. During the first months, data will be used to produce point-estimates of these proportions (e.g., patients seen by GP, correct triage decisions, all false positives, type 1 false positives, patients left without being seen, etc.). With increasing duration of the study, incoming data will be used to explain variability of these probabilities in terms of patient background characteristics, operating nurses/emergency physician, season, etc. Statistical assistance will be called for in order to conduct these analyses.

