For research question 12 we will perform a multivariate regression analysis, explaining the expenditures (dependent variable) with three sets of explanatory variables: general background characteristics of the patient (age, sex, insurance status), diagnostic information (urgency code, chosen eMTS flowchart) and system characteristics (occupancy rate ED, time of the day, triage nurse, intervention or control weekend). The coefficient for the dummy variable indicating an intervention weekend then gives the impact of the extended triage. It should confirm the effect found in 8. The inclusion of control variables, when estimating the impact in our regression, however reduces residual standard deviation and thus improves the precision

of the estimate. The coefficients on the other variables give a further insight in the additional determinants of expenditures. The regression analyses will be performed on the computer of the data manager using STATA.

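### The tests of the intervention effect on expenditure specify no adjustment for weekend clustering, although weekends are the randomised unit

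*Combined protocol and SAP*

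**What the plan says.** Under Design of the clinical trial, the protocol concludes that only weekends can be randomised. The section Methodology for the financial aspects accepts this design: "we will make use of a cluster randomized trial to get an unbiased estimate of the difference in expenditures".

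The same section then sets out the tests:

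- **RQ9** (average expenditure per patient): "We will calculate the averages and use a t-test to test statistical significance".
- **Expenditure by type of care**: another t-test. The text labels it research question 10, but its content (consultation fees, imaging, clinical biology) is RQ11 as listed under Research questions.
- **RQ10.1 and 10.2** (green/blue and red/orange patients): expenditures per patient are calculated, and the plan is to "compare them between the intervention and control weekends, using a t-test to test for statistical difference".
- **RQ12**: a multivariate regression on patient characteristics, diagnostic information and "system characteristics (occupancy rate ED, time of the day, triage nurse, intervention or control weekend". Of the treatment effect it says: "The coefficient for the dummy variable indicating an intervention weekend then gives the impact of the extended triage".

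None of these analyses names a weekend random effect, a cluster-robust standard error or a weekend-level summary. Methodology for the medical aspect does recognise that patients are nested in weekends and calls for a mixed model, but it opens that paragraph with "The parameters of interest in questions 1 through 8 are (conditional) proportions, which calls for analysis by a non-linear model".

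**The concern.** The intervention varies only between weekends. Anything that moves costs for a whole weekend (staffing, case mix, crowding, season) therefore enters the error of the comparison once per weekend, not once per patient. A patient-level t-test, or an ordinary regression on patient records, treats some 52 weekends as several thousand independent observations.

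For RQ12 the plan discusses precision only through the residual: "The inclusion of control variables, when estimating the impact in our regression, however reduces residual standard deviation and thus improves the precision". That is correct for patient-level noise but says nothing about variation between weekends. Nurse and occupancy covariates may absorb part of that variation, but they do not replace a weekend term.

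At stake is the formal hypothesis, under Financial aspect, that extended triage lowers expenditure for the health insurance system and the patient. Ordinary weekend-to-weekend variation could be declared a significant cost difference more often than 5% of the time. The concern is limited to the intervention effect. RQ12 coefficients for covariates that vary only within weekends, such as sex, are largely unaffected.

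**Working it through.** The plan gives no power calculation, SD or ICC for expenditure, so there is no figure of its own to reproduce. The check asks how far the type I error of a nominal 5% two-sided patient-level test could move.

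**Inputs from the documents**
- 8000 weekend presentations in 2016 (Recruitment strategy) and about 15 exclusions per weekend (Inclusion and Exclusion): 8000/52 − 15 = 138.8 eligible patients per weekend, before admitted patients are removed.
- All weekends of one year (Sample size): about 52.
- One control weekend per month (Introduction, aim of the project): 12 control and 40 intervention weekends.

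**Assumptions**
- Ambulatory patients per weekend: m = 110, with m = 30 and m = 15 for smaller subgroups.
- ICC from 0.001 to 0.05.
- Share s of the weekend variance that is common to a month, which one control per month largely balances out: 0, 0.5 or 0.8.

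**Formulas**
- DEFF = (1 − ICC) + m·ICC·(1 − s) + 0.0154·m·ICC·s. With s = 0 this is 1 + (m − 1)·ICC.
- The factor 0.0154 is the imbalance left because some months have four weekends and some five. With 8 months of 3 and 4 months of 4 intervention weekends, it is [8(1/12 − 3/40)² + 4(1/12 − 4/40)²] / (1/12 + 1/40) = 0.0154.
- Type I error = 2[1 − Φ(1.96/√DEFF)].

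**Example** (m = 110, ICC 0.01, s = 0.5): DEFF = 0.99 + 0.55 + 0.0085 = 1.548; 1.96/√1.548 = 1.575; type I error 11.5%.

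**Type I error (%) of the patient-level t-test**

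| m | s | ICC 0.001 | 0.005 | 0.01 | 0.02 | 0.05 |
|---|---|---|---|---|---|---|
| 110 | 0 | 6.3 | 11.5 | 17.5 | 27.2 | 44.0 |
| 110 | 0.5 | 5.6 | 8.3 | 11.5 | 17.6 | 31.1 |
| 110 | 0.8 | 5.3 | 6.3 | 7.6 | 10.3 | 17.8 |
| 30 | 0 | 5.3 | 6.7 | 8.4 | 11.9 | 21.0 |
| 30 | 0.5 | 5.2 | 5.8 | 6.7 | 8.4 | 13.4 |
| 30 | 0.8 | 5.1 | 5.3 | 5.6 | 6.3 | 8.2 |
| 15 | 0.5 | 5.1 | 5.4 | 5.8 | 6.5 | 8.9 |

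Design of the clinical trial words the allocation differently (one control in relation to every four intervention weekends). Reading it as equal blocks of four or five weekends changes little: at m = 110, s = 0.5 the row becomes 5.6, 8.2, 11.4, 17.4, 30.8.

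**Simulation, skewed (lognormal) costs, no effect.** At m = 110, s = 0.8, the patient-level t-test rejected in 5.2, 5.9, 7.8, 10.6 and 17.4% of runs, in line with the formula. Across the simulated t-test settings, weekend means with month terms gave 4.6–5.3%, and a plain t-test on weekend means 0.2–5.2%. That plain test is valid, but conservative when variance is shared within months.

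**Simulation of RQ12.** Settings: m = 110; 15 nurses, 4 per weekend; occupancy carrying half of the weekend variance (all assumed). Rejection (%) for the intervention coefficient at ICC 0.001, 0.01, 0.05:

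| Method | s = 0 | s = 0.5 |
|---|---|---|
| No weekend term | 5.0, 11.7, 30.1 | 4.7, 8.8, 18.7 |
| Weekend random intercept (REML) + month, 38 df | 3.2, 5.3, 4.4 | 3.2, 4.5, 4.6 |
| Ordinary cluster-robust (CR1) + month | 11.1, 11.8, 11.9 | 11.0, 11.9, 9.3 |
| Jackknife cluster-robust (CR3) + month | 2.2, 2.7, 2.0 | 2.2, 2.2, 2.4 |

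In the same model the test for sex rejected in 4.1–5.9% of runs, so it shows no inflation.

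**The case against.** The strongest reply is that the financial section never names the unit of the t-test. Calculating averages and then testing them could mean a test on weekend averages, which would respect the design. For RQ12 the section is silent on standard errors and does not assert independence, and the statement about nesting in the medical section describes the whole design. The ambiguity is real. However, the text speaks of expenditures per patient, RQ12 is plainly fitted to patient records, and the only modelling remedy offered is confined to questions 1 to 8. Even on the favourable reading, the unit still has to be written down.

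Second, the magnitude rests on assumptions. With one hospital and one cooperative, the weekend ICC may be tiny, and at ICC 0.001 the error is near nominal. This stands: the size is conditional, although the omission is not.

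Third, the failure of ordinary cluster-robust errors arises mostly from adding month terms. Without them, simulated rejection was 3.6–5.1% (s = 0.5) and 6.6–7.6% (s = 0). The jackknife alternative is conservative, which costs power. Both points are fair, but they concern a fallback option and not the main remedy.

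Finally, the analysis is secondary and meant "to get a first insight in the changes in resource use due to the extended triage". That limits the severity. It does not make the planned significance tests valid.

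**Conclusion.** The concern holds. On its natural reading, the plan tests the expenditure effect with standard errors that omit between-weekend variance, in a trial that the same section calls cluster randomised.

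For all ambulatory patients (assumed m = 110), the type I error of a nominal 5% t-test runs from 5.3% (ICC 0.001, 80% of weekend variance at month level) to 44.0% (ICC 0.05, none at month level). In subgroups of about 15 per weekend, with half the variance at month level, it is 5.1–8.9%. For the RQ12 intervention coefficient, the simulated range is 4.7–30.1%. ICC, ambulatory share, subgroup sizes, month share and the nurse and occupancy structure are all assumed. Restriction on holidays was not simulated.

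Point estimates are not biased by this, and the primary question already has a mixed model. This should be fixed, but it does not threaten the trial's main conclusion.

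**What to change.** In Methodology for the financial aspects, replace the t-tests for RQ9, 10.1, 10.2 and 11 with one pre-specified choice:

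- (a) a linear mixed model for expenditure per patient, with a weekend random intercept and small-sample degrees of freedom; or
- (b) a regression on weekend mean expenditures, weighted by weekend size so that it targets expenditure per patient, as RQ9 asks.

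In either case:

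- Include the blocks or factors actually used to restrict the randomisation (for example month or season, holidays). State which they were, because the two descriptions of the control-weekend schedule can be read as different blocks.
- For RQ12, add a weekend random intercept with small-sample degrees of freedom and the same factors. If cluster-robust errors are preferred alongside block terms, name a bias-reduced or jackknife version and accept that the jackknife is conservative.
- Report the weekend ICC for expenditure, and correct the research-question numbers in the section.

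**Cost.** The change needs wording and a little code. Weekend and month follow from the arrival time already collected; holiday status also needs a calendar. Standard errors will usually be wider than from the patient-level t-test. Month terms use degrees of freedom: 52 − 12 − 1 = 39 remain. In return, they recover power when variance is shared within months. For an effect of 0.1 SD at ICC 0.01 and m = 110, simulated power with weekend means plus month terms was 71.4%, against 60.4% for a plain t-test on weekend means (s = 0.5). With no month-level variance it was 58.8% against 59.0%. Options (a) and (b) weight weekends differently, so the choice must be made in advance.
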